## **6.2        IMPORTANT PROTOCOL DEVIATIONS**

Consistency check listings (for identification of deviations from time windows) and a list of protocol deviations (e.g. deviations in drug administration, in blood sampling times, etc.) will be provided to be discussed at the Report Planning Meeting. At this meeting, it will be decided whether a discrepant data value can be used in analyses or whether it must be corrected in the clinical database. Each protocol deviation must be assessed to determine whether it is an iPD. For definition of iPDs, and for the process of identification of these, refer to the BI reference document "Identify and Manage Important Protocol Deviations (iPD)" ([2](#)).

If any iPDs are identified, they are to be summarised into categories and will be captured in the minutes of the Report Planning Meeting via an accompanying Excel spreadsheet ([3](#)). Categories which are considered to be iPDs in this trial are defined in the integrated quality and risk management plan (IQRMP). If the data show other iPDs, the definition in the IQRMP will be supplemented accordingly by the time of the Report Planning Meeting.

iPDs will be summarized and listed. [Table 6.2: 1](#) below specifies which kind of iPDs could potentially lead to exclusion from which analysis set. The decision on exclusion of patients from analysis sets will be made at the latest at the Report Planning Meeting, after discussion of exceptional cases and implications for analyses.

Table 6.2: 1 Handling of iPDS

iPD code	iPD Category & Brief Description	Excluded from which analysis set
iPD B1	Informed consent not available/not done	All
iPD B2	Informed consent too late	None
iPD A1	Inclusion Criteria not met	PKS, PDS, PETS
iPD A2	Exclusion Criteria met	PKS, PDS, PETS
iPD C1	Randomisation not followed	Not applicable
iPD C2	Non-compliance	PKS, PDS, PETS
iPD C3	Incorrect intake of trial medication	PKS, PDS, PETS
iPD D1	Prohibited medication use	PKS, PDS, PETS
iPD D2	Improper washout of concomitant medication	PKS, PDS, PETS
iPD E1	Certain violations of procedures used to measure primary or secondary data	PKS, PDS, PETS
iPD F1	Certain violations of time schedule used to measure primary or secondary data	PKS, PDS, PETS
iPD G1	PDs affecting safety and rights of subjects	PKS, PDS, PETS

### 6.3 SUBJECT SETS ANALYSED

Statistical analyses will be based on the following analysis sets:

- Treated set (TS): The treated set includes all subjects who were treated with at least one dose of study drug. The treated set will be used for safety analyses.
- Pharmacokinetic parameter analysis set (PKS): This set includes all subjects in the treated set (TS) who provide at least one PK endpoint and was not excluded due to a protocol deviation relevant to the evaluation of PK or due to PK non-evaluability (as specified in the following subsection ‘Pharmacokinetics’). Thus, a subject will be included in the PKS, even if he/she contributes only one PK parameter value to the statistical assessment. Analyses of PK parameters will be based on the PKS.
- Pharmacodynamic analysis set (PDS): This set includes all subjects in the treated set (TS) who provide at least one post-baseline measurement of MAO-B inhibition in

platelet rich plasma which were not excluded due to a protocol deviation relevant to the evaluation of PD.

- PET set (PETS): This set includes all subjects in the treated set (TS) who provide at least one PET scan at baseline and one on-treatment, i.e. the reduction in MAO-B availability can be calculated for at least one post-baseline measurement (either 14 or 28 or 42 days)

The following Table 6.3: 1 contains the information which subject is used for which class of endpoint:

Table 6.3: 1 Subject sets analyzed

Class of endpoint	Subject set			
	TS	PETS	PDS	PKS
Primary endpoint		X		
Secondary MAO-B availability from PET scan endpoints		X		
Secondary MAO-B inhibition in platelet rich plasma endpoint			X	
Secondary PK endpoints				X
Safety parameters & treatment exposure	X			
Demographic/baseline endpoints	X			
Important protocol deviations	X			

## **6.5 POOLING OF CENTRES**

This section is not applicable, because the study is performed in only one centre.

## **6.6 HANDLING OF MISSING DATA AND OUTLIERS**

Data of screened subjects who were withdrawn from the trial prior to first administration of investigational study drug will not be reported in the CTR.

Data of subjects who drop out or withdraw from the trial will be reported in the CTR as far as their data are available. All withdrawals will be documented and the reason for withdrawal reported in the CTR.

**CTP Section 7.5.1:** *It is not planned to impute missing values for safety parameters.*  
One exception where imputation might be necessary for safety evaluation are AE dates.  
Missing or incomplete AE dates are imputed according to BI standards.

**CTP Section 7.5.2:** *PK parameters that cannot be reasonably calculated based on the available drug concentration-time data will not be imputed.*  
Missing data and outliers of PK data are handled according to BI standards ([4](#)).

## 6.7 BASELINE, TIME WINDOWS AND CALCULATED VISITS

A separate baseline is defined for each study treatment. The baseline is the last available value before first administration of BI 1467335.

Time windows are defined in Section 6.1 of the CTP. Adherence to time windows will be checked at the Report Planning Meeting.

Unscheduled measurements of laboratory data or vital signs data will be assumed to be repeat measurements of the most recent scheduled measurement (e.g. for follow-up or confirmation of a particular value). Therefore, unscheduled measurements will be assigned to the planned time point of the previous scheduled measurement.

Descriptive statistics of laboratory data will be calculated by planned time point based on the worst value of the subject at that planned time point (or assigned to that planned time point). For vital signs, descriptive statistics will be calculated by planned time point based on the last value of the subject at that planned time point (or assigned to that planned time point).

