5.2.6.1.4 Adverse events of special interest

The term adverse events of special interest (AESI) relates to any specific AE that has been identified at the project level as being of particular concern for prospective safety monitoring and safety assessment within this trial, e.g. the potential for AEs based on knowledge from other compounds in the same class. AESIs need to be reported to the sponsor’s Pharmacovigilance Department within the same timeframe that applies to SAEs, please see [Section 5.2.6.2.2](#).

The following are considered as AESIs:

- Hepatic injury

A hepatic injury is defined by the following alterations of hepatic laboratory parameters:

- o An elevation of AST (aspartate transaminase) and/or ALT (alanine transaminase) ≥ 3 -fold ULN combined with an elevation of total bilirubin ≥ 2 -fold ULN measured in the same blood sample, or
- o Aminotransferase (ALT, and/or AST) elevations ≥ 10 fold ULN

These lab findings constitute a hepatic injury alert and the subjects showing these lab abnormalities need to be followed up according to the ‘DILI checklist’ provided in the eDC system. In case of clinical symptoms of hepatic injury (icterus, unexplained encephalopathy, unexplained coagulopathy, right upper quadrant abdominal pain, etc.) without lab results (ALT, AST, total bilirubin) available, the Investigator should make sure that these parameters are analysed, if necessary in an unscheduled blood

Proprietary confidential information © 2019 Boehringer Ingelheim International GmbH or one or more of its affiliated companies

test. Should the results meet the criteria of hepatic injury alert, the procedures described in the DILI checklist should be followed.

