7.3.4 Safety analyses

Safety will be analysed based on the assessments described in [Section 2.2.2.2](#). All treated subjects (TS, refer to [Section 7.2](#)) will be included in the safety analysis. Safety analyses will be descriptive in nature and based on BI standards. No hypothesis testing is planned.

Proprietary confidential information © 2019 Boehringer Ingelheim International GmbH or one or more of its affiliated companies

For all analyses, the treatment actually administered (= treatment at onset) to the subject will be used (any deviations from the randomised treatment will be discussed in the minutes of the Report Planning Meeting).

Treatments will be compared in a descriptive way. Tabulations of frequencies/proportions will be used to evaluate categorical (qualitative) data, and tabulations of descriptive statistics will be used to analyse continuous (quantitative) data.

Measurements (such as ECG, vital signs, or laboratory parameters) or AEs will be assigned to treatments (see [Section 4.1](#)) based on the actual treatment at the planned time of the measurement or on the recorded time of AE onset (concept of treatment emergent AEs). Therefore, measurements planned or AEs recorded prior to first intake of trial medication will be assigned to the screening period, those between first trial medication intake and end of REP (which corresponds to the patient's individual end of treatment; see [Section 1.2.2](#)) will be assigned to the treatment period. These assignments including the corresponding time intervals will be defined in detail in the TSAP. Note that AEs occurring after the last per protocol contact but entered before final database lock will be reported to Pharmacovigilance only and will not be captured in the trial database.

Additionally, further treatment intervals (analysing treatments) may be defined in the TSAP in order to provide summary statistics for time intervals, such as combined treatments, on-treatment totals, or periods without treatment effects (such as screening and follow-up intervals).

Adverse events will be coded using the Medical Dictionary for Regulatory Activities (MedDRA). Frequency, severity, and causal relationship of AEs will be tabulated by treatment, system organ class, and preferred term. SAEs, AESIs (see [Section 5.2.6.1](#)), and other significant AEs (according to ICH E3) will be listed separately.

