## 6. GENERAL ANALYSIS DEFINITIONS

### 6.1 TREATMENTS

For basic study information on treatments to be administered, assignment of treatment groups, and selection of doses, cf. Section 4 of the CTP.

Each subject is planned to be treated daily over a period of 4 or 6 weeks with BI 1467335 film-coated tablets:

Table 6.1: 1 Dosage and treatment schedule

Substance	Formulation	Unit strength	Dosage
BI 1467335	Film-coated tablet	10 mg	2 tablets (5 mg) qd for 28 days
BI 1467335	Film-coated tablet	3 mg	3 tablets (1 mg) qd for 42 days

In addition to the two investigational treatments stated above, the following non-investigational PET tracer will be used:

- PET tracer (NIMP)  
≤ 100 µg [C]-L-deprenyl-D2 as solution for injection for a predose assessment and about 1,5 h after dosing of BI 1467335 on Day 14 (10 mg dose group only), Day 28 and Day 42 (3 mg dose group only).

For statistical analyses of AEs, the following separate analysis phases will be defined for each subject:

Table 6.1: 2 Analysis phases for statistical analysis of AEs

Study analysis phase	Label	Start	End
Screening	Screening	Date of informed consent	Date/time of first administration of BI 1467335
On treatment	BI 1467335	Date/time of first administration of BI 1467335	12:00 a.m. on day after subject's end of study participation date.

In CTR Section 15, AE displays will be presented for the on-treatment phase only.

In CTR Section 15, AE tables, the following totals will be provided in addition:

- "Total on treatment", defined as the total over all on-treatment phases

AEs during the screening phase will be listed in CTR Section 16.2 but not tabulated.

Statistical analyses of safety laboratory tests and vital signs will be conducted with clear differentiation between baseline (cf. [Section 6.7](#)) and on-treatment measurements.

More details on the technical implementation of these analyses are provided in the ADS Plan of this TSAP.

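### SAP 6.7 files unscheduled labs and vital signs taken soon after first dose under the pre-dose Day 1 time point

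*SAP*

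**What the plan says.** SAP 6.7 says that unscheduled labs and vital signs "will be assumed to be repeat measurements of the most recent scheduled measurement", and so "unscheduled measurements will be assigned to the planned time point of the previous scheduled measurement". By-time-point statistics for labs are then "based on the worst value of the subject at that planned time point (or assigned to that planned time point"), and those for vital signs are "based on the last value of the subject at that planned time point (or assigned to that planned time point"). The same section defines baseline with a cut at first dose: "The baseline is the last available value before first administration of BI 1467335".

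Protocol 7.3.4 places measurements by their planned time and sends those planned before first intake to the screening period. It leaves the detail to the SAP: "These assignments including the corresponding time intervals will be defined in detail in the TSAP". SAP 6.1 supplies date/time phases for adverse events only: "For statistical analyses of AEs, the following separate analysis phases will be defined for each subject". For labs and vital signs, SAP 6.1 states an aim of clearly separating baseline from on-treatment values and refers to an ADS Plan for technical implementation.

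On subjects who are never dosed, protocol 3.3.4 keeps the data of anyone leaving before first dose out of the CRF and the CTR, and SAP 6.6 keeps them out of the CTR. Protocol 5.2.6.2.1 requires adverse events on the CRF from consent onwards, with screening failures as the only exception.

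**The concern.** The carry-back rule suits a genuine repeat taken at or near the scheduled visit. It does not suit a value drawn after dosing has started when the previous scheduled measurement was before dosing. Such a value is an on-treatment observation whatever prompted it.

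Nor is every unscheduled test a repeat. When symptoms of liver injury appear without available results, protocol 5.2.6.1.4 says "the Investigator should make sure that these parameters are analysed, if necessary in an unscheduled blood" test. Between first dose and Day 14 no routine labs are scheduled, so an unscheduled test is the only laboratory information from that period, and the rule tabulates it as pre-dose.

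What is at stake is the by-time-point safety summary: a Day 1 row that is no longer pre-dose, and on-treatment rows that omit an early finding. The protocol's placement by planned time compounds this, because a value given a pre-dose planned time would go to screening.

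The minor point concerns an eligible subject who has the predose PET scan with arterial cannulation and then leaves by choice before the first dose of BI 1467335. For a non-serious adverse event in that subject, the documents give two answers on CRF entry and CTR reporting.

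**Working it through.** The plan gives no figure to reproduce here, and protocol 7.7 states that no precision or power calculation was made. The check applies the SAP 6.7 rule to the schedule.

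**Inputs.** Flow Charts, footnote 2: Day 1 labs and vital signs are planned at -2:00 h, before dosing. Flow Charts and Table 5.2.3: 1: the next routine labs are on Day 14 (312 h) in both groups; the 3 mg laboratory entry on Day 7 is drug, alcohol and cotinine screening only. Flow Charts: the next vital signs are on Day 4 (72 h) at 10 mg and Day 7 (144 h) at 3 mg. Protocol 7.7: 5 subjects per group.

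**Window in which a post-dose value falls back to Day 1 pre-dose.** This is the time from first dose to the next scheduled measurement: labs 312/24 = 13 days in both groups; vital signs 72/24 = 3 days (10 mg) and 144/24 = 6 days (3 mg).

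**Share of the treatment course.** The on-treatment phase of SAP 6.1 is taken from Day 1 09:00 to the midnight ending the EoTrial day, assuming participation ends at that visit:
- 10 mg (Day 33 to 36): 33 - 0.375 = 32.625 to 36 - 0.375 = 35.625 days.
- 3 mg (Day 47 to 50): 47 - 0.375 = 46.625 to 50 - 0.375 = 49.625 days.

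| | Share of dosing days | Share of on-treatment phase |
|---|---|---|
| Labs, 10 mg | 13/28 = 46% | 13/35.625 to 13/32.625 = 36% to 40% |
| Labs, 3 mg | 13/42 = 31% | 13/49.625 to 13/46.625 = 26% to 28% |
| Vital signs, 10 mg | 3/28 = 11% | 3/35.625 to 3/32.625 = 8% to 9% |
| Vital signs, 3 mg | 6/42 = 14% | 6/49.625 to 6/46.625 = 12% to 13% |

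These are window lengths, not event rates.

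**Effect of one value on the Day 1 row (n = 5, all values assumed).** The mean shifts by (new value - replaced value)/5. For labs the replacement happens if the later value is worse; for vital signs it always happens, since the last value is used.
- ALT 25 in all five pre-dose, one unscheduled Day 8 value of 150: mean (4 × 25 + 150)/5 = 50; SD √[(4 × 25² + 100²)/4] = √3125 = 55.9; maximum 150. The true row is 25, 0 and 25. The median stays at 25.
- With spread: pre-dose 20, 22, 25, 28, 30 (mean 25, SD √(68/4) = 4.1), and an unscheduled Day 5 value of 90 in the subject at 25: mean 190/5 = 38, SD √(3448/4) = 29.4, median 28.
- Systolic pressure 120 in all five pre-dose, one unscheduled Day 2 value of 160: mean (4 × 120 + 160)/5 = 128; SD √[(4 × 8² + 32²)/4] = √320 = 17.9; maximum 160. The true row is 120, 0 and 120.

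If the Day 1 row were also shown for difference from baseline, it would read +25, +13 and +8 in the three examples instead of 0. SAP 7.8.2 does not say whether that row is shown.

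**After the change.** If the look-back stops at first dose, the window is 0 hours in both groups for both types of measurement.

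**Never-dosed subjects.** Flow Chart footnote 13 allows the predose PET scan only once all screening procedures are complete and the subject is considered eligible. A subject who has that scan and then withdraws by choice is not naturally a screening failure, so 5.2.6.2.1 calls for CRF entry of an adverse event while 3.3.4 forbids it. The conflict with SAP 6.6 on the CTR follows by implication. A failed Day -1 test may be read as a screening failure, whose data are still collected at the site.

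**The case against.** The best defence is that the SAP already states the right intention. SAP 6.1 asks for clear separation of baseline and on-treatment values, SAP 6.7 cuts baseline at first dose, and a programmer who respected both might never file a post-dose value under Day 1. The ADS Plan may contain an explicit split, and some SAP section numbers are absent from the public text, so what those sections held cannot be known. The Day 1 distortion also assumes a row built from all values assigned to Day 1; if that row is simply the defined baseline, the fault shrinks to an early value with no summary row.

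Nor is safety information lost. SAP 7 lists every individual value, clinically relevant findings after first dose are analysed as adverse events, and liver alerts have their own table. The frequency tables compare baseline with the last value on treatment, which would normally be a later scheduled one. The rate of unscheduled tests is unknown and the numerical examples are invented.

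Most of this limits the consequence and is accepted. It does not remove the fault. The aim in SAP 6.1 gives no placement rule; the one placement rule in the text is the carry-back, which works against that aim. The baseline cut protects the baseline value but not the by-time-point rows. An unseen plan may resolve the matter, but 6.7 as written does not.

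On the minor point, the documents do not define a screening failure, and SAP Table 6.1: 2 runs the screening phase up to first dose. A broad reading could therefore bring every never-dosed subject within the exemption. Footnote 13 points the other way, so the wording still needs reconciling.

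**Conclusion.** The concern holds. As written, SAP 6.7 sends unscheduled labs from the 13 days after first dose, and unscheduled vital signs from the first 3 days (10 mg) or 6 days (3 mg), to a pre-dose time point. One such value moves a five-subject Day 1 mean by a fifth of its excess and is missing from the on-treatment rows. This should be corrected, but it does not threaten the trial's main conclusions.

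The conclusion rests on three conditions: SAP 6.7 is applied as worded, the ADS Plan adds no split, and at least one unscheduled value falls in the window. How often the last would happen cannot be estimated from the documents. If the Day 1 row is built from the defined baseline alone, only the omission from the on-treatment rows remains.

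The inconsistency on adverse events of never-dosed subjects is real but minor. It is clear only for eligible subjects who had the tracer and cannulation and left for a reason other than screening failure; their number is not given and may be zero.

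**What to change.** In SAP 6.7, add that no laboratory or vital-sign value taken after the first dose of BI 1467335 may be assigned to a pre-dose time point, and say where such values are summarised on treatment. A worst on-treatment row would serve for labs. If the ADS Plan already imposes this split, state it in 6.7. The cost is one sentence and minor programming.

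Separately, align protocol 3.3.4, protocol 5.2.6.2.1 and SAP 6.6 so that adverse events of eligible, tracer-exposed, never-dosed subjects are handled the same way in all three. If tracer-exposed screening failures are also to be covered, the exemption in 5.2.6.2.1 must change too. This is wording only, but the protocol part needs the approvals described in protocol 8.1. Neither change adds a procedure for subjects.

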## 7. PLANNED ANALYSIS

The format of the listings and tables will follow the standards defined in the BI standards with the exception of those generated for PK-calculations (6).

The individual values of all subjects will be listed. Listings will be sorted by treatment, subject number and visit (if visit is applicable in the respective listing). AE listings will be sorted by assigned treatment (see [Section 7.8.1](#) below for details). The listings will be contained in Appendix 16.2 (SDL) of the CTR.

The following standard descriptive statistical parameters will be displayed in summary tables of continuous variables:

N	number of non-missing observations
Mean	arithmetic mean
SD	standard deviation
Min	minimum
Median	median
Max	maximum

For plasma concentrations as well as for all PK parameters the following descriptive statistics will additionally be calculated:

CV	arithmetic coefficient of variation
gMean	geometric mean
gCV	geometric coefficient of variation

For PD parameters the CV (arithmetic coefficient of variation) will additionally be calculated.

The data format for descriptive statistics of plasma concentrations will be identical with the data format of the respective concentrations. The descriptive statistics of PK parameters will be calculated using the individual values with the number of decimal places as provided by the evaluation program. Then the individual values as well as the descriptive statistics will be reported with three significant digits in the CTR.

Tabulations of frequencies for categorical data will include all possible categories and will display the number of observations in a category as well as the percentage (%) relative to the respective treatment group. Percentages will be rounded to one decimal place. The category missing will be displayed if and only if there actually are missing values. Percentages will be based on all subjects in the respective subject set whether they have non-missing values or not.

## 7.1 DEMOGRAPHIC AND OTHER BASELINE CHARACTERISTICS

Only descriptive statistics are planned for this section of the report.

